## Human Subjects Research – Protocol Form

### **Guidelines for completing this research protocol:**

- Please submit typed applications via email. Handwritten forms and hard copy forms will not be accepted.
- For items and questions that do not apply to the research, indicate as “not applicable.”
- Provide information for all other items clearly and avoid using discipline specific jargon.
- Please only include text in the provided boxes. The text boxes will expand as they are typed in to accommodate large amounts of text.

**Before submitting this application, ensure that the following have been completed.**

- Protocol Form is complete.
- Relevant CITI modules have been completed for all members of the research team at [www.citiprogram.org](http://www.citiprogram.org).
- Informed consent/assent/parental permission document(s) are provided.
- Relevant waivers and appendices are provided.
- Recruitment materials are provided.
- Research materials (e.g. surveys, interview guides, etc.) are provided.
- Any relevant letters of support are provided.

Instructions on the non-exempt review process and guidance to submitting applications, can be found on the OPRS [website](#). You may also contact OPRS by email at [[contact]](mailto:[contact]) or phone at [contact].

**Submit completed applications via email to:** [[contact]](mailto:[contact]).

## Section 2. RESEARCH TEAM

2A. Are there other investigators engaged in the research?  Yes (include a Research Team Form )  No
2B. If yes, are any of the researchers not affiliated with Illinois?  Yes  No

## Section 3. PROTOCOL TITLE

Video Technology-based Social Engagement
--

## Section 4. FUNDING SOURCE

4A. Is the research funded?  Research is not funded and is not pending a funding decision (Proceed to Section 5).  Research is funded (funding decision has been made).  Funding decision is pending . Funding proposal submission date:
4B. Indicate the source of the funding.  University of Illinois Department, College or Campus, please specify :  Federal, please specify : National Institutes of Health

 Commercial Sponsorship & Industry  , please specify:
 State of Illinois Department or Agency, please specify:
 Other, please specify:
4C. Sponsor-assigned grant number, if known: 2 R44 AG059450-02A1
4D. A complete copy of the funding proposal or contract is attached.
 Attached, please specify title: Enhancing Quality of Life for Older Adults With and Without MCI through Social Engagement Over Video Technology
4E. Funding Agency Official To Be Notified of IRB Approval (if Applicable)
Name:
Agency:
E-mail:
Phone:

## Section 5. CONFLICTS OF INTEREST

**Please indicate below whether any investigators or members of their immediate families have any of the following.** If the answer to any of the following items is yes, please submit the University of Illinois approved conflict management plan. If you have any questions about conflicts of interest, contact [[contact]](mailto:[contact]).

**5A.** Financial interest or fiduciary relationship with the research sponsor (e.g. investigator is a consultant for the research sponsor).  Yes  No

**5B.** Financial interest or fiduciary relationship that is related to the research (e.g. investigator owns a startup company, and the intellectual property developed in this protocol may be useful to the company).  Yes  No

**5C.** Two or more members of the same family are acting as research team members on this protocol.

Yes  No

## Section 6. SUMMARY & PURPOSE OF RESEARCH

**6A. In lay language, summarize the objective and significance of the research.**

The goal of this project is to test the efficacy of a social engagement intervention delivered using a video-technology called OneClick for older adults with and without mild cognitive impairment (MCI). Following the baseline assessment, participants will be randomized into two groups: Group 1 (intervention first), or Group 2 (intervention later). Group 1 will receive 8 weeks of the OneClick social engagement intervention, during which time Group 2 will receive no planned intervention. Both groups will receive an assessment at 4 weeks and another assessment at 8 weeks after they are enrolled in the study. Group 2 will then be rolled into the OneClick social engagement intervention. They will receive 8 weeks of the OneClick social

 Clarify whether or not sponsor requires specific language in the contractual agreement that impacts human subjects research

 Clarify whether or not the sponsor requires the protocol adhere to ICH GCP (E6) standards

engagement intervention, similar to Group 1, and will be assessed after four weeks and 8 weeks of participating in the video chat intervention. We will test the benefits of using OneClick over 8 weeks by measuring social engagement, quality of life, and user acceptance of technology.

Older adults are at risk of social isolation, and therefore, negative health and quality-of-life outcomes. For individuals with MCI, social activities and engagement may slow disease progression and the transition into dementia. Social engagement technologies offer a novel opportunity to connect people to enhance social interactions. OneClick's existing platform connects people from across the country and world over shared interests in live, small group video conversations. In distinct contrast to existing social media and online chat, dating, or meet-up platforms, OneClick connects people virtually without the need to exchange private information or download an application. Users of different ages, including older adults, have reported positive experiences using OneClick. Our prior feasibility and usability studies have shown that older adults with and without MCI are interested in and will use computer technology and the internet for personal enjoyment. In an initial project funded by a SBIR Phase I (R43AG069450) grant from NIA, we optimized the OneClick platform for use by older adults with and without MCI (Protocol #18585 and #19145) and completed an experiential field trial to assess usability (Protocol #19271). The current project, funded by a SBIR Phase II grant (2 R44 AG059450-02A1), will test the efficacy of the OneClick social engagement intervention in a larger randomized control trial (RCT) using a wait-list control group design.

**6B. Indicate if your research includes any of the following:**

- Secondary data (use of data collected for purposes other than the current research project)
- Data collected internationally (include [International Research Form](#))
- Translated documents (include [Certificate of Translation Form](#) and translated documents)
- Research activities will take place at Carle (include documentation (email or letter) from Carle stating that the review of your [Research Services Request Form](#) is complete)

**6C. Letters of support from outside institutions or entities that are allowing recruitment, research, or record access at their site(s) are attached.  Yes  Not Applicable**

## Section 7. PROCEDURES

**7A. Select all research methods and/or data sources that apply.**

- Surveys or questionnaires, *select all that apply:*  Paper  Telephone  Online
- Interviews
- Focus groups
- Field work or ethnography
- Standardized written, oral, or visual tests
- Taste or smell testing

- Intervention or experimental manipulation
- Exercise and muscular strength testing
- Noninvasive procedures to collect biological specimens (e.g., hair and nail clippings, saliva, etc.)
- Noninvasive procedures to collect physiological data (e.g., physical sensors, electrocardiography, etc.)
- Procedures involving radiation
- Recording audio and/or video and/or taking photographs
- Recording other imaging
- Materials that have already been collected or already exist, *specify source of data:*
- [HIPAA-protected data](#)
- [FERPA-protected data](#)
- [GDPR-protected data](#)
- Other, *please specify:*

**7B. List all testing instruments, surveys, interview guides, etc. that will be used in this research.**

Telephone screening DRAFT  
Modified Telephone Interview for Cognitive Status (TICS-M)  
Modified Techsage Background Questionnaire (TBSQ)  
Montreal Cognitive Assessment (MoCA)  
Geriatric Depression Scale (GDS)  
Instrumental Activities of Daily Living (IADL)  
Mobile Device Proficiency Questionnaire (MDPQ-16)  
Computer Proficiency Questionnaire (CPQ)  
Logical Memory  
Friendship Scale  
UCLA Loneliness Scale- Version 3  
Quality of Life- AD  
System Usability Scale  
Perceived Ease of Use and Usefulness  
Interpersonal Support Evaluation List  
Intention Survey  
Lubben Social Network Index  
Session Feedback Questions DRAFT  
Opinion Interview DRAFT  
Category Fluency  
Social Activity Frequency (SAQ)

**Drafts or final copies of all research materials are attached.**  Yes

**7C. List approximate study dates.** Date of IRB approval- August 1, 2024

**7D. What is the duration of participants' involvement?** Participants' eligibility will be determined following a phone pre-screening and a video screening. If eligible, participants will be randomized into an

immediate social engagement intervention group or a later intervention group after a 1-hour baseline assessment.

**Group 1 (intervention first):** Participants in this group will receive 8 weeks of the OneClick social engagement intervention. During this 8-week period, they will be asked to participate in 2 social engagement intervention sessions per week each lasting approximately 45 minutes. A mid-assessment will be done 4 weeks after the beginning of the intervention, and a final post-assessment after 8-weeks of intervention. Both assessments will take 1 hour. Participants will additionally complete a 30-45 minute phone interview at 4 and 8 weeks.

**Group 2 (intervention later):** After being placed in Group 2, participants will receive no planned intervention in the first 8 weeks. They will complete one assessment after 4 weeks and another after 8 weeks. Both sessions will last 1 hour. Then participants will be rolled into the OneClick social engagement intervention lasting 8 weeks. They will complete two additional assessments, one 4 weeks and the other 8 weeks after beginning the video chat intervention. These assessments will last 1 hour. Participants will additionally complete a 30-45 minute phone interview at 12 and 16 weeks.

## 7E. How many times will participants engage in research activities?

**Group 1** will complete three assessments: baseline; week 4 post-video chat participation; and week 8 post-video chat participation. They will attend 16 OneClick event sessions.

**Group 2** will complete five assessments: baseline; week 4 after enrollment and before video chat intervention; week 8 after enrollment and before video chat intervention; week 4 post-video chat participation; and week 8 post-video chat participation. They will attend 16 OneClick event sessions.

## 7F. Narratively describe the research procedures in the order in which they will be conducted.

1. Phone Pre-Screening: All participants will undergo a phone screening to determine initial eligibility for the next step (video screening). The phone screening will gather information about basic demographics, living arrangements, and visual and auditory acuity. TICS-M will be administered to screen for global cognition. Participants who meet the initial eligibility criteria will be invited to participate in a video screening.
2. Informed Consent for Video Screening: Electronic informed consent will be obtained from all participants using REDCap to participate in a screening session over videochat. The participants with MCI will have no deficits in global cognitive functioning, as determined by TICS-M. Subtle cognitive changes observed in these individuals do not impact their ability to provide informed consent; therefore, no proxy consent will be required.
3. Video Screening: After obtaining online informed consent, participants will complete a background questionnaire (TSBQ). The Montreal Cognitive Assessment (MoCA) will be administered to assess global cognition. The Geriatric Depression Scale (GDS) will be administered to screen for elevated depressive symptoms. Researchers will review and determine final eligibility for participation. Those who meet eligibility will be invited to participate in the study. If they agree to participate, they will be consented for the intervention study before administering baseline assessment. If a participant does not qualify or prefers not

to participate despite being eligible, they will be thanked for their participation. The session will last approximately 45 minutes. All participants regardless of eligibility will be paid \$15 for the video screening session.

4. Informed Consent for RCT: Electronic informed consent will be obtained from all participants using REDCap for the RCT. Details about the study, expectations, risks, and benefits will be described. All questions will be clarified, and comprehension of the information will be checked by using the teach-back approach. The participants with MCI will have no deficits in global cognitive functioning. Subtle cognitive changes observed in these individuals do not impact their ability to provide informed consent; therefore, no proxy consent will be required.
5. Baseline Assessment: Baseline assessment will include participant characterization measures and intervention outcome measures. The session will last approximately one hour.
6. Randomization process: The randomization process is designed to achieve appropriate generation of the random allocation sequence and concealment of the allocation sequence. A researcher who is not involved in phone screening, video screening, or informed consent will generate the randomization list prior to the screening of the first person for the randomized, controlled trial. The randomization list will use computer-generated random numbers. The randomization list will be stratified with random permuted blocks. The stratification variable will be Mild Cognitive Impairment (MCI present versus absent). MCI will be defined by a MoCA score of 20-25. The block size will vary randomly between 4 and 6. Research personnel who perform phone screening, video screening, informed consent, or assessments will not be able to access the randomization list. After a potential participant has completed phone screening and video screening, has fulfilled all inclusion criteria, has demonstrated no exclusion criteria, has provided documented informed consent, and has completed baseline assessment, the researcher will unconceal the randomization assignment for the intervention: Group 1 (intervention first) versus Group 2 (intervention later). After assignment, the participant and the researcher who performed informed consent will not be blinded to group allocation.
7. Participants in Group 2 will be told they will begin the intervention 8 weeks later and in the meantime will be asked to complete assessments at 4 and 8 weeks after joining the study but before beginning the video chat participation. Participants in Group 1 will be given information about the general research expectations over the next 8 weeks and will be invited to sign up for a technology training session to learn how to use the OneClick system.
8. Technology training session: Participants ready to begin the video chat participation will complete a brief technology training session. To help schedule the technology training participants will be contacted by a researcher through their preferred method of communication. Once the technology training is scheduled, participants will be sent a reminder the day prior to their session. A researcher will provide an overview of the purpose and functionality of the OneClick system. A help card will be mailed to the participants with reminders about OneClick login, event sign-up, and participation. It will list a telephone number and email address that can be used for questions or difficulties. One of our research team members will help setup the computer as needed before the 8-week trial if the participant is

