**8C. Who is the prime recipient of funding, if funded? University of Illinois at Urbana-Champaign**

**8D. What is the management and communication plan for information that might be relevant to the protection of research subjects (e.g. unanticipated problems involving risks to subjects, interim results, and protocol modifications)?** This is a multi-site, minimal risk clinical trial and as such will be monitored by an independent Safety Officer. The Principal Investigator (PI) [name] with support from [name] will be responsible for ensuring participants' safety on a daily basis. A Safety Officer (SO) has been appointed to provide data and safety monitoring oversight to monitor participant safety, evaluate the progress of the study, and review procedures for maintaining the confidentiality of data, quality of data collection, management, and analyses. [name], Associate Chair for Research, Department of Medicine, University of Illinois College of Medicine at Peoria will serve as the SO. [name] has extensive RCT experience. He is an internist with additional training in clinical trial methodology. He has 25 years of experience as a clinical trial investigator, including roles as Principal Investigator of federally-funded research grant protocols. [name] has served as a member of the Data Safety and Monitoring Boards for various clinical trials.

No adverse events are expected given that this is a behavioral intervention study of low risk involving use of computer/tablet to engage in conversations with other people over a video chat platform called OneClick. Nevertheless, we do have a protocol in place for documenting and reporting any events to the safety officer (SO).

Formal responses to alerts and adverse events will be followed by research staff immediately upon learning about such an event. When an adverse event is identified by a member of the research team, the event will be reported to the PI within 24 hours and recorded on the Adverse Event Form. The University of Illinois will be responsible for maintaining the events forms and submitting reports or summaries to the SO.

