## Section 9. SUBJECT ENROLLMENT GOAL & EQUITABLE SELECTION OF SUBJECTS

**9A. For each performance site, indicate the estimated total number of participants.**

Performance Site	# Male	# Female	Total
#1 UIUC	53	53	106
#2 CJE Senior Life	35	35	70

#3			
TOTALS	88	88	176
If additional performance sites are included on an attachment, check here: 			
9B. Select all participant populations that will be recruited.			
Age:			
 Adults (18+ years old)  Minors ( $\leq$ 17 years old)  Specific age range, please specify : 65 and older			
Gender:			
 No targeted gender (both men and women will be recruited/included)  Targeted gender, please indicate :  Men/boys  Women/girls  Other, please specify :			
Race/Ethnicity:			
 No targeted race or ethnicity (all races and ethnicities will be recruited/included)  Targeted race or ethnicity, please specify :			
College Students:			
 No targeted college population  UIUC general student body  Targeted UIUC student population, provide the instructor or course information, name of the departmental subject pool, or other specific characteristics :  Students at institution(s) other than UIUC, please specify :			
Any research with students on UIUC's campus needs to be registered with the Office of the Dean of Students .			
Other:			

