**11C. For each group of participants, describe the details of the recruitment process.**

We will use our well-established multi-pronged recruitment strategies, which include word-of-mouth, email, and telephone scripts to members of established registries; flyers and brochures shared by community organizations and partners; advertisements in newspapers and newsletters; and personal visits to community events. All recruitment materials will be pre-approved by the IRB.

**At UIUC:** Participants with and without MCI will be recruited through the **I-HELP registry** and **[name] registry** of persons with MCI. The Human Factors and Aging Laboratory directed by [name] is part of a consortium that coordinates a registry of potential older research participants through the Beckman Institute at UIUC called I-HELP (Illinois Health and Engagement Lifespan Project). The I-HELP registry

currently contains 522 individuals including individuals with a diagnosis of MCI who are interested in participating in university research. [name] has a registry of individuals with MCI who are interested in participating in research studies. The MCI registry was developed by [name] research affiliation and ongoing MCI studies with the Carle Neuroscience Institute, which sees approximately 100 MCI patients per year. Additionally, interested participants will be recruited from Carle Neuroscience Institute in collaboration with [name], Staff Neurologist at Carle Hospital.

**At CJE:** CJE Senior Life supports about 20,000 older adults, which includes individuals with MCI, who live in independent living communities. Participants with and without MCI will be recruited from the 8 retirement community sites managed by CJE SeniorLife as well as their extensions. All sites are independent living. Sites in this study have been purposefully selected throughout the Chicagoland area to reflect a range of racial/ethnic backgrounds to maximize generalizability of findings. Recruitment flyers will be placed in resident mailboxes. Additionally, residents will receive a recruitment flyer during community town-hall meetings.

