Identifiers: NCT05380180

Brief Title: Enhancing Quality of Life for Older Adults With and Without Mild Cognitive Impairment (MCI) Through Social Engagement Over Video Technology

Document Date: Sept 4, 2023

Statistical Analysis Plan

To measure the main effects of the intervention on primary and secondary outcomes, irrespective of the cognitive status, the OneClick intervention Group will be compared to the Waitlist group at (i) mid-assessment (4 weeks) compared with the baseline assessment, and (ii) post-assessment (8 weeks) compared with baseline assessment. In addition, we will perform a separate analysis of covariance with age and cognitive ability (MoCA and Logical Memory - Delayed Recall) as covariates. We plan to implement an intent-to-treat analysis where all participants who were allocated to either the intervention or waitlist group will be included in the analysis, regardless of the number of sessions attended or their completion of assessments.

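### Two sites with different recruitment sources, but site is in neither the stratification nor the SAP analyses, so chance site imbalance is neither prevented nor adjusted for, at a modest cost in precision

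*Protocol*

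**What the plan says.** **Sites.** Protocol Section 8D states: "This is a multi-site, minimal risk clinical trial". The enrolment table in Section 9A reads (site number, men, women, total) "1 UIUC 53 53 106" and "2 CJE Senior Life 35 35 70".

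**Recruitment.** Under Section 11C, UIUC draws on two research registries and on a neuroscience institute. For CJE the text is: "Participants with and without MCI will be recruited from the 8 retirement community sites managed by CJE SeniorLife as well as their extensions". Section 9C gives each site its own clinical supervisor for study personnel.

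**Randomisation.** Section 7F step 6 says "The randomization list will be stratified with random permuted blocks", then "The stratification variable will be Mild Cognitive Impairment (MCI present versus absent"), then "The block size will vary randomly between 4 and 6". It speaks of one list, to be generated before the first person is screened. It does not say outright whether the sites share that list.

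**Analysis.** The SAP compares the arms at 4 and 8 weeks, each relative to baseline and irrespective of cognitive status. It adds: "we will perform a separate analysis of covariance with age and cognitive ability (MoCA and Logical Memory - Delayed Recall) as covariates". Site does not appear in either analysis.

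**The concern.** The outcomes listed in Section 6A include social engagement and quality of life, and step 10 of Section 7F adds loneliness and isolation. People found through research registries or a clinic may change differently over eight weeks on such measures from people found in retirement communities. If so, site is prognostic for change. Balancing on MCI does little to balance site, so the arms can end up with different site mixes.

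Two things are at stake. Between-site variance stays in the error term, which widens the confidence interval. And if a visible imbalance arises, adding site after the data have been seen is a post-hoc choice that is open to challenge. Site is known for everyone before randomisation, so both can be avoided cheaply.

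**Working it through.** **Inputs from the documents.** UIUC 106, CJE 70, total 106 + 70 = 176 (Section 9A). Blocks of 4 to 6, stratified by MCI only (Section 7F step 6). The documents give no alpha, power, target effect, SD, allocation ratio or site effect, so there is no plan figure to reproduce beyond the sum.

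**Assumptions.** 1:1 allocation (88 per arm), two-sided 5% test, within-site SD of change = 1, MCI share 30% to 70%, site difference in change *s* = 0.2 to 0.5 SD, with 0.8 SD as an extreme.

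**1. How large is the imbalance?** With p = 70/176 = 0.398, p(1 − p) = 0.2395.

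- SD of the arm difference in CJE share = √(4 × 0.2395 / 176) = 0.074, or 7.4 points.
- The exact hypergeometric calculation, ignoring MCI strata, gives P(difference ≥ 10 points) = 0.166 and P(≥ 15 points) = 0.045.
- Simulation of the planned method (MCI strata, blocks of 4 or 6, 5,000 runs per setting) gives:

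| MCI share, UIUC / CJE | SD (points) | P(> 10 points) | P(> 15 points) |
|---|---|---|---|
| 50% / 50% | 7.5 | 16.6% | 5.4% |
| 30% / 30% | 7.5 | 17.5% | 5.0% |
| 70% / 30% | 6.8 | 12.7% | 3.1% |

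Stratifying by MCI therefore removes little site imbalance. For comparison, stratifying by site as well would cut the SD to about 1.2 points.

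**2. What does it do to the estimate?** The contribution is the difference in CJE share times *s*. A 10-point gap shifts the estimate by 0.10 × 0.2 = 0.02 SD up to 0.10 × 0.5 = 0.05 SD. The standard error of the effect is √(4/176) = 0.151 SD, so the larger shift is one third of a standard error.

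**3. How much variance does site explain?** R² = p(1 − p)s² / (1 + p(1 − p)s²).

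- s = 0.2: 0.0096 / 1.0096 = 0.9%
- s = 0.5: 0.0599 / 1.0599 = 5.7%
- s = 0.8: 0.1533 / 1.1533 = 13.3%

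**4. What does adjustment gain?** At 88 per arm, an effect of 0.425 SD has 80% power when sites do not differ, so it serves as the reference effect. Simulation with 4,000 runs per setting (error about 0.6 points for power, 0.3 for type I error) gives:

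| s | Power without site | Power with site | Type I error without site | Type I error with site |
|---|---|---|---|---|
| 0.2 | 79.8% | 80.2% | 5.4% | 5.3% |
| 0.5 | 76.9% | 78.9% | 5.9% | 5.8% |
| 0.8 | 75.8% | 81.0% | 4.7% | 4.8% |

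The gain is 0.4 and 2.0 points over the assumed range, and about 5 points at the extreme. Mean estimates stay at the true value throughout. The 5.9% is not a cost of leaving site out, because the adjusted model gives 5.8% on the same simulated trials.

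**5. Could a different effect at CJE be detected?** The standard error of the site-by-arm interaction is √(4/106 + 4/70) = 0.31 SD. With the usual multiplier of 2.80, 80% power needs a difference of about 0.86 SD between the site-specific effects.

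**The case against.** A reader might infer that site imbalance passes directly into the treatment effect and biases it. The documents do not support that. Imbalance under randomisation is chance, the unadjusted standard error covers it, and type I error is the same with and without site. The SAP also compares each visit with baseline. It does not say how baseline enters, but in a change comparison stable differences in level between sites cancel, and only differences in change carry over. The ANCOVA on age, MoCA and delayed recall would absorb any site difference that runs through age or cognition. All of this stands.

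A reader might also infer that CJE participants live communally and UIUC participants do not. Section 11C describes all CJE sites as independent living, and Section 10A sets the same independence, cognitive and depression criteria for everyone. Step 1 of Section 7F records living arrangements person by person, which is a more direct measure than site. Assessments at weeks 4 and 8 are by video or phone, and the events run on one online platform. The contrast in recruitment source is documented. A contrast in daily social life is plausible only.

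Nor do the documents show that the primary outcomes are the social ones. The SAP refers to primary and secondary outcomes without naming them.

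What the objection leaves in place is the omission: site is in neither the list nor the models, and including it costs almost nothing.

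**Conclusion.** The point holds as a small, inexpensive improvement. It does not show a threat to validity. Site imbalance of 10 points or more is fairly common (about 13% to 17% of trials), but its consequence is limited: site explains about 1% to 6% of the variance, and adjustment gains about 0 to 2 points of power if the sites differ in eight-week change by 0.2 to 0.5 SD. That range is an assumption and decides the result. With no site difference in change there is nothing to gain, and at 0.8 SD the gain would be about 5 points. The figures also assume 1:1 allocation and full enrolment of 106 and 70.

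A by-site comparison cannot be counted as a benefit. At these numbers it could reliably detect only a very large difference in effect between sites.

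**What to change.** In the SAP, before outcome data are examined:

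- Include site (UIUC, CJE) and the stratification factor MCI (present, absent) as fixed covariates in the between-group comparison at 4 and 8 weeks.
- Add site to the ANCOVA, which already carries MoCA.
- Label any arm difference shown by site as descriptive.
- State whether one randomisation list served both sites or each site had its own.

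The cost is a sentence or two in the SAP and one degree of freedom for each added term, with no new data or staff. Stratifying the list by site would prevent the imbalance, but it is probably no longer possible because Section 7F step 6 has the list generated before the first screening. The covariate does not depend on it.
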